11.6.3.3 Guideline for assessing exacerbations that increase in severity

If an exacerbation begins as moderate but becomes severe, the exacerbation should be captured as severe.

11.6.4 Onset and Resolution of COPD Exacerbations:

The date of onset is the first day of the worsening of signs and symptoms of COPD exacerbation.

The date of resolution is when the Investigator and/or patient ascertain the signs and symptoms have returned to pre-exacerbation levels or to a new baseline.

The date of onset and the date of resolution will be recorded in the eCRF.

11.6.5 Treatment of COPD Exacerbations

11.6.5.1 Guidelines for Treatment with Corticosteroids

- The duration of treatment with oral/systemic corticosteroids should be less than or equal to 14 days (dose and type according to local practice).
- The duration of treatment with oral/systemic corticosteroids greater than 14 days should be discussed with the Medical Monitor and Sponsor to determine if the patient should remain in the study.
- Any course of oral/systemic corticosteroids started within 7 days of finishing a previous course will be considered as treatment for a single exacerbation.

11.6.5.2 Guidelines for Treatment with Antibiotics

If there is evidence of respiratory infection that warrants treatment with antibiotics in the opinion of the Investigator or treating physician, the following guidelines should be used:

- The duration of treatment with antibiotics should be 7 to 14 days (dose and type according to local practice). If first antibiotic treatment fails and additional antibiotics are warranted, the total duration of antibiotic treatment should not exceed 30 days. If the duration of treatment with antibiotics needs to be greater than 30 days, the Investigator or treating physician should discuss the patient with the Medical Monitor and Sponsor to determine if the patient should remain in the study.
- Any course of antibiotics started within 7 days of finishing a previous course will be considered as treatment for a single exacerbation.

Use of antibiotics for the treatment of upper or lower respiratory tract infections is not considered a COPD exacerbation unless the patient experiences worsening of signs and symptoms associated with exacerbations as given above.

11.6.6 Recording COPD Exacerbations

Exacerbation details will be recorded in the exacerbation form of the eCRF. COPD exacerbations will not be recorded as adverse events (AE), unless they meet the definition of a serious adverse event (SAE). Pneumonia details will be recorded in the Pneumonia form of the eCRF and will also be recorded as an AE or SAE. Pneumonia should be confirmed by chest-x-ray. Every effort should be made to obtain a chest x-ray within 48 hours suspected pneumonia.

11.6.7 Study Continuation or Withdrawal Due to COPD Exacerbation

- Patients who experience a single COPD exacerbation during the treatment period may remain in the study and should continue to take their blinded study medication if possible and record their symptoms and rescue albuterol/salbutamol usage in their eDiary.
- Patients who experience a second COPD exacerbation and/or a severe COPD exacerbation that requires in-patient hospitalization will be discontinued from study treatment (Section 7.0).

11.7 Appendix 7: Adverse Events: Definitions and Procedures for Recording, Evaluating, Follow-up and Reporting

Definition of AE

- An AE is any untoward medical occurrence in a patient or subject, temporally associated with the use of blinded study medication, whether or not considered related to the blinded study medication.
- NOTE: An AE can therefore be any unfavorable and unintended sign (including an abnormal laboratory finding), symptom, or disease (new or exacerbated) temporally associated with the use of blinded study medication.

Events Meeting the AE Definition

- Any abnormal laboratory test results (eg, hematology, clinical chemistry) or other safety assessments (eg, ECG, radiological scans, vital signs measurements), including those that worsen from baseline, considered clinically significant in the medical and scientific judgment of the Investigator (ie, not related to progression of underlying disease).
- Exacerbation of a chronic or intermittent pre-existing condition including either an increase in frequency and/or intensity of the condition.
- New conditions detected or diagnosed after blinded study medication administration even though it may have been present before the start of the study.
- Signs, symptoms, or the clinical sequelae of a suspected drug-drug interaction.
- Signs, symptoms, or the clinical sequelae of a suspected overdose of either blinded study medication or a concomitant medication. Overdose per se will not be reported as an AE/SAE unless it is an intentional overdose taken with possible suicidal/self-harming intent. Such overdoses should be reported regardless of sequelae.
- “Lack of efficacy” or “failure of expected pharmacological action” per se will not be reported as an AE or SAE. Such instances will be captured in the efficacy assessments. However, the signs, symptoms and/or clinical sequelae resulting from lack of efficacy will be reported as an AE or SAE if they fulfil the definition of an AE or SAE.

Events NOT Meeting the AE Definition

- Any clinically significant abnormal laboratory findings or other abnormal safety assessments which are associated with the underlying disease, unless judged by the Investigator to be more severe than expected for the patient's condition.
- The disease/disorder being studied or expected progression, signs, or symptoms of the disease/disorder being studied, unless more severe than expected for the patient's condition.
- Medical or surgical procedure (eg, endoscopy, appendectomy): the condition that leads to the procedure is the AE.
- Situations in which an untoward medical occurrence did not occur (social and/or convenience admission to a hospital).
- Anticipated day-to-day fluctuations of pre-existing disease(s) or condition(s) present or detected at the start of the study that do not worsen.

Definition of SAE

If an event is not an AE per definition above, then it cannot be an SAE even if serious conditions are met (eg, hospitalization for signs/symptoms of the disease under study, death due to progression of disease).

An SAE is defined as any untoward medical occurrence that, at any dose:

a) Results in death**b) Is life-threatening**

The term 'life-threatening' in the definition of "serious" refers to an event in which the patient was at risk of death at the time of the event. It does not refer to an event, which hypothetically might have caused death, if it were more severe.

c) Requires inpatient hospitalization or prolongation of existing hospitalization

In general, hospitalization signifies that the patient has been detained (usually involving at least an overnight stay) at the hospital or emergency ward for observation and/or treatment that would not have been appropriate in the physician's office or outpatient setting. Complications that occur during hospitalization are AEs. If a complication prolongs hospitalization or fulfills any other serious criteria, the event is serious. When in doubt as to whether "hospitalization" occurred or was necessary, the AE should be considered serious.

Hospitalization for elective treatment of a pre-existing condition that did not worsen from baseline is not considered an AE.

d) Results in persistent disability/incapacity

- The term disability means a substantial disruption of a person's ability to conduct normal life functions.
- This definition is not intended to include experiences of relatively minor medical significance such as uncomplicated headache, nausea, vomiting, diarrhea, influenza, and accidental trauma (eg, sprained ankle) which may interfere with or prevent everyday life functions but do not constitute a substantial disruption.

e) Is a congenital anomaly/birth defect**f) Other situations:**

Medical or scientific judgment should be exercised in deciding whether SAE reporting is appropriate in other situations such as important medical events that may not be immediately life-threatening or result in death or hospitalization but may jeopardize the patient or may require medical or surgical intervention to prevent one of the other outcomes listed in the above definition. These events should usually be considered serious.

Examples of such events include invasive or malignant cancers, intensive treatment in an emergency room or at home for allergic bronchospasm, blood dyscrasias or convulsions that do not result in hospitalization, or development of drug dependency or drug abuse.

Recording and Follow-up of AE and/or SAE**AE and SAE Recording**

- When an AE/SAE occurs, it is the responsibility of the Investigator to review all documentation (eg, hospital progress notes, laboratory reports, and diagnostics reports) related to the event.
- The Investigator will then record all relevant AE/SAE information in the eCRF. Each event must be recorded separately.
- It is **not** acceptable for the Investigator to send photocopies of the patient's medical records to Sponsor/Sponsor's designee in lieu of completion of the Verona Pharma /AE/SAE eCRF page.
- There may be instances when copies of medical records for certain cases are requested by groups such as the Sponsor/Sponsor's designee, Health Authority, or Ethics Committee. In this case, all patient identifiers, with the exception of the subject/patient number, will be redacted on the copies of the medical records before submission to records to the Sponsor/Sponsor's designee.
- The Investigator will attempt to establish a diagnosis of the event based on signs, symptoms, and/or other clinical information. Whenever possible, the diagnosis (not the individual signs/symptoms) will be documented as the AE/SAE.

Assessment of Intensity

The Investigator will make an assessment of intensity for each AE and SAE reported during the study and assign it to one of the following categories:

- Mild: An event that is easily tolerated by the patient, causing minimal discomfort and not interfering with everyday activities.
- Moderate: An event that causes sufficient discomfort and interferes with normal everyday activities.
- Severe: An event that prevents normal everyday activities. An AE that is assessed as severe should not be confused with a SAE. Severe is a category utilized for rating the intensity of an event; and both AEs and SAEs can be assessed as severe.

An event is defined as ‘serious’ when it meets at least one of the predefined outcomes as described in the definition of an SAE, NOT when it is rated as severe.

Assessment of Chronicity

- Single occasion: Single event with limited duration.
- Intermittent: Several episodes of an event, each of limited duration
- Persistent: Event which remained indefinitely.

Assessment of Causality

- The Investigator is obligated to assess the relationship between blinded study medication and each occurrence of each AE/SAE. The AE must be characterized as unrelated, unlikely to be related, possibly related, probably related, or unknown (unable to judge).
 - “Probably related” conveys that there are facts, evidence, and/or arguments to suggest a causal relationship, rather than a relationship cannot be ruled out.
 - “Possibly related” suggests that the association of the AE with the blinded study medication is unknown; however, the AE is not reasonably supported by other conditions.
 - “Unlikely to be related” suggests that only a remote connection exists between the blinded study medication and the AE. Other conditions, including chronic illness, progression or expression of the disease state or reaction to concomitant therapy, appear to explain the reported AE.
 - “Unrelated” is used if there is not a reasonable possibility that the blinded study medication caused the AE.
 - All efforts should be made to classify the AE according to the above categories. The category “unknown” (unable to judge) may be used only if the causality is not assessable (eg, because of insufficient evidence, conflicting evidence, conflicting data, or poor documentation).
- The Investigator will use clinical judgment to determine the relationship.

- Alternative causes, such as underlying disease(s), concomitant therapy, and other risk factors, as well as the temporal relationship of the event to blinded study medication administration will be considered and investigated.
- The Investigator will also consult the Investigator's Brochure (IB) in his/her assessment.
- For each AE/SAE, the Investigator must document in the medical notes that he/she has reviewed the AE/SAE and has provided an assessment of causality.
- There may be situations in which an SAE has occurred and the Investigator has minimal information to include in the initial report to the Sponsor/Sponsor's designee. However, it is very important that the Investigator always make an assessment of causality for every event before the initial transmission of the SAE data to the Sponsor/Sponsor's designee.
- The Investigator may change his/her opinion of causality in light of follow-up information and send a SAE follow-up report with the updated causality assessment.
- The causality assessment is one of the criteria used when determining regulatory reporting requirements.

Action and Outcome

- Action taken with blinded study medication (none, blinded study medication stopped, blinded study medication temporarily interrupted)
- Other actions (none, concomitant medication, study discontinuation, hospitalization, other)
- The outcome and date of outcome according to the following definitions:
 - Recovered or resolved (adverse event disappeared)
 - Recovered or resolving (patient is recovering)
 - Not recovered or not resolved (adverse event remains without signs of improvement)
 - Recovered or resolved with sequelae (adverse event has resulted in permanent disability or incapacity)
 - Fatal
 - Unknown (only applicable if patient has been lost to follow-up)
- Seriousness (yes or no)

Follow-up of AEs and SAEs

- The Investigator is obligated to perform or arrange for the conduct of supplemental measurements and/or evaluations as medically indicated or as requested by the Sponsor/Sponsor's designee to elucidate the nature and/or causality of the AE or SAE as fully as possible. This may include additional laboratory tests or investigations, histopathological examinations, or consultation with other health care professionals.
- If a patient dies during participation in the study or during a recognized follow-up period, the Investigator will provide the Sponsor/Sponsor's designee with a copy of any postmortem findings including histopathology.
- New or updated information will be recorded in the originally completed eCRF.

- The Investigator will submit any updated SAE data to the Sponsor/Sponsor's Designee within 24 hours of receipt of the information.

Reporting of SAEs

SAE Reporting to the Sponsor/Sponsor's designee via an Electronic Data Collection Tool

- The primary mechanism for reporting an SAE to the Sponsor/Sponsor's designee will be the electronic data collection tool.
- If the electronic system is unavailable, then the study center will use the paper SAE data collection tool (see next section).
- The study center will enter the SAE data into the electronic system as soon as it becomes available.
- After the study is completed at a given study center, the electronic data collection tool will be taken off-line to prevent the entry of new data or changes to existing data.
- If a study center receives a report of a new SAE from a patient or receives updated data on a previously reported SAE after the electronic data collection tool has been taken off-line, then the study center can report this information on a paper SAE form (see next section) or to the Medical Monitor/SAE coordinator by telephone.
- Contacts for SAE reporting can be found in Section 11.2 on the Medical Monitor Contact Information page.

SAE Reporting to Sponsor/ Sponsor's Designee via Paper CRF if eCRF is not available

- If the eCRF is not available, facsimile transmission of the SAE paper CRF may be used to transmit this information to the Medical Monitor or the SAE coordinator.
- In rare circumstances and in the absence of facsimile equipment, notification by telephone is acceptable with a copy of the SAE data collection tool sent by overnight mail or courier service.
- Initial notification via telephone does not replace the need for the Investigator to complete and sign the SAE CRF pages within the designated reporting time frames.
- Contacts for SAE reporting can be found in Section 11.2 on the Medical Monitor Contact Information page.

11.8 Appendix 8: Contraceptive Guidance and Collection of Pregnancy Information

Definitions:

Woman of Childbearing Potential (WOCBP)

A woman is considered fertile following menarche and until becoming postmenopausal unless permanently sterile (see below).

Women in the following categories are not considered WOCBP

1. Premenarchal: Note premenarchal females **ARE NOT ELIGIBLE TO PARTICIPATE** in this study.
2. Premenopausal female with 1 of the following:
 - a) Documented hysterectomy.
 - b) Documented bilateral salpingectomy.
 - c) Documented bilateral oophorectomy. Note: Documentation can come from the study center personnel's: review of the patient's medical records, medical examination, or medical history interview.
3. Postmenopausal female:
 - a) Postmenopausal females are defined as amenorrhoeic for greater than 1 year with an appropriate clinical profile, eg, age appropriate, > 45 years, in the absence of hormone replacement therapy.

Contraception Guidance

Male Patients

- Male patients with female partners of childbearing potential are eligible to participate if they agree to ONE of the following from the first dose up to 30 days after the last dose of study medication:
 - Are abstinent from penile-vaginal intercourse as their usual and preferred lifestyle (abstinent on a long-term and persistent basis) and agree to remain abstinent.
 - Agree to use a male condom plus partner use of a contraceptive method with a failure rate of < 1% per year as described in Table 14 when having penile-vaginal intercourse with a woman of childbearing potential who is not currently pregnant.
- In addition, male patients must refrain from donating sperm for the duration of the study and for 30 days after the last dose of study medication.
- Male patients with a pregnant or breastfeeding partner must agree to remain abstinent from penile-vaginal intercourse or use a male condom during each episode of penile penetration during the study and for 30 days after the last dose of study medication.

Female patients

Female patients of childbearing potential are eligible to participate if they are not breastfeeding and agree to use a highly effective method of contraception consistently and correctly as described in the table below. during the study starting at Visit 1 and for at least 30 days after the last dose of study treatment.

Table 14: Highly Effective Contraceptive Methods

| |
|---|
| 
Highly Effective Contraceptive Methods That Are User Dependent ^a
 
Failure rate of < 1% per year when used consistently and correctly.
 |
| 
Combined (estrogen and progestogen containing) hormonal contraception associated with inhibition of ovulation^b
 
 • Oral • Intravaginal • Transdermal |
| 
Progestogen only hormonal contraception associated with inhibition of ovulation
 
 • Oral • Injectable |
| 
Highly Effective Contraceptive Methods That Are User Independent ^a
 |
| 
Implantable progestogen only hormonal contraception associated with inhibition of ovulation^b
 
 • Intrauterine device (IUD) • Intrauterine hormone-releasing system (IUS) 
Bilateral tubal occlusion.
 |
| 
Vasectomized partner
 
A vasectomized partner is a highly effective birth control method provided that the partner is the sole male sexual partner of the WOCBP and the absence of sperm has been confirmed. If not, an additional highly effective method of contraception should be used.
 |
| 
Sexual abstinence
 
Sexual abstinence is considered a highly effective method only if defined as refraining from heterosexual intercourse during the entire period of risk associated with the study treatment. The reliability of sexual abstinence needs to be evaluated in relation to the duration of the study and the preferred and usual lifestyle of the patient.
 |
| 
NOTES:
 
^a Typical use failure rates may differ from those when used consistently and correctly. Use should be consistent with local regulations regarding the use of contraceptive methods for patients participating in clinical studies.
 |

Table 14: Highly Effective Contraceptive Methods

^bHormonal contraception may be susceptible to interaction with the study treatment, which may reduce the efficacy of the contraceptive method. In this case, 2 highly effective methods of contraception should be utilized during the treatment period and for at least 30 days after the last dose of study treatment.

Pregnancy Testing:

- WOCBP should only be included after a negative highly sensitive pregnancy test.
- Additional pregnancy testing should be performed at times specified in the SoA (Section 1.3).

Pregnancy testing should be performed whenever a menstrual cycle is missed or when pregnancy is otherwise suspected.

Collection of Pregnancy Information***Male patients with partners who become pregnant***

The Investigator will attempt to collect pregnancy information on any male patient's female partner who becomes pregnant while the male patient is in the study. This applies only to male patients who receive ensifentrine.

After obtaining the necessary signed informed consent from the pregnant female partner directly, the Investigator will record pregnancy information on the appropriate form and submit it to the Sponsor within 24 hours of learning of the partner's pregnancy. The female partner will also be followed to determine the outcome of the pregnancy. Information on the status of the mother and child will be forwarded to the Sponsor. Generally, the follow-up will be no longer than 6 to 8 weeks following the estimated delivery date. Any termination of the pregnancy will be reported regardless of fetal status (presence or absence of anomalies) or indication for the procedure.

Female Patients who become pregnant

- The Investigator will collect pregnancy information on any female patient who becomes pregnant while participating in this study. Information will be recorded on the appropriate form and submitted to the Sponsor within 24 hours of learning of a patient's pregnancy.
- The patient will be followed to determine the outcome of the pregnancy. The Investigator will collect follow-up information on the patient and the neonate and the information will be forwarded to the Sponsor. Generally, follow-up will not be required for longer than 6 to 8 weeks beyond the estimated delivery date. Any termination of pregnancy will be reported, regardless of fetal status (presence or absence of anomalies) or indication for the procedure.
- While pregnancy itself is not considered to be an AE or SAE, any pregnancy complication or elective termination of a pregnancy will be reported as an AE or SAE. A spontaneous abortion is always considered to be an SAE and will be reported as such.

- Any post-study pregnancy related SAE considered reasonably related to the blinded study medication by the Investigator will be reported to the Sponsor as described in Section 8.7.5. While the Investigator is not obligated to actively seek this information in former patients, he or she may learn of an SAE through spontaneous reporting.
- Any female patient who becomes pregnant while participating in the study will discontinue blinded study medication and be withdrawn from the study.

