2.3 Benefit/Risk Assessment

No significant medical risks to patients have been identified from studies conducted thus far with ensifentrine administered in the solution formulation, suspension formulation, or dry powder formulation. A slight increase in mean heart rate (up to 12 beats per minute [bpm]) without reported medical significance at a 6 mg suprathreshold doses has been reported in healthy volunteers (RPL554-PK-101). In patients with COPD, transient increases in peak heart rate of 3 bpm vs placebo have been observed with the 6 mg twice daily dose only over 4 weeks. Otherwise, non-clinical and clinical data to date do not indicate any areas of particular medical safety concern.

Effects on reproductive performance in male rats given the highest dose of 15.5 mg/kg/day included lower number of pairings of dosed males resulting in pregnancy in undosed females, higher pre and post implantation loss resulting in lower mean litter size, and lower sperm motility and higher abnormal sperm. No ensifentrine-related adverse effects were observed at 5.75 mg/kg/day (20.5 times the maximum recommended human dose based on area under the curve [AUC]). There were no effects on embryo-fetal survival and development in either rats or rabbits in the main embryo-fetal development studies. Ensifentrine had no effects on fertility or reproductive performance in female rats.

Ensifentrine has statistically and clinically significant bronchodilator as well as anti-inflammatory effects. As such, the clinical development of ensifentrine is focused on the treatment of obstructive and inflammatory lung diseases, including COPD.

Considering the consistent improvements in lung function, symptoms, and health-related quality of life across multiple studies in patients with COPD and the overall favorable safety profile in studies to date, the benefit/risk profile of ensifentrine is considered positive.

More detailed information about the known and expected benefits and risks and reasonably expected AEs of ensifentrine can be found in the Verona Pharma plc. Ensifentrine Clinical IB v. 20.0, 2021 (or more current version, if applicable).

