Patients completing the run-in period and meeting all entry and Randomization Criteria will be randomized. The two different stratification factors will be applied at randomization. Details on blinded study medication and administration are provided in Section 6.0. The Study Schematic is shown in Section 1.2.

During the treatment period, patients will complete all assessments and procedures as outlined in the Schedule of Activities (Section 1.3) for 24 weeks. Patients completing treatment will complete a Follow-Up within 4 to 10 days of the last scheduled study visit.

Patients meeting the withdrawal criteria during the study or who withdraw from the study for other reasons will be discontinued and requested to complete the Early Termination/ Withdrawal Procedures and complete a Follow-Up within 4 to 10 days of the Early Termination/ Withdrawal Visit.

Patients who permanently discontinue double blind study medication may remain in the study and follow the assessments and procedures as noted in Section 7.2.

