8.5.10.3 Determination of Drug Concentration

Samples for the determination of plasma PK for ensifentrine will be analyzed on behalf of the Sponsor using appropriate validated analytical methods. Full details of the bioanalytical methods will be described in a separate Bioanalytical Report. All samples from patient assigned to treatment with ensifentrine during the study that are within the known stability of ensifentrine at the time of planned analysis by the bioanalytical laboratory will be analyzed; samples obtained from placebo patients will not be analyzed. Drug concentration information that may unblind the study will not be reported to study centers or blinded personnel until the study has been unblinded. Only the bioanalytical laboratory and unblinded biostatistician(s) who generate the randomization schedule may be unblinded to patient treatment assignment prior to database lock (DBL).

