8.7.5 Pregnancy

- Details of all pregnancies in female patients will be collected after the start of blinded study medication and until 30 days after the last dose of blinded study medication.
- If a pregnancy is reported, the Investigator should inform the Sponsor within 24 hours of learning of the pregnancy and should follow the procedures outlined in Section 11.8.
- Abnormal pregnancy outcomes (eg spontaneous abortion, fetal death, stillbirth, congenital anomalies, ectopic pregnancy) are considered SAEs.

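### Appendix 8 limits partner-pregnancy reports to men on ensifentrine, which a blinded investigator cannot know, and captures new pregnancies only until study exit, short of the 30-day post-dose contraception period

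*Protocol*

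**What the plan says.** Section 11.8 (Appendix 8, Collection of Pregnancy Information) sets three conditions for partners of male patients:

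- Timing: it covers a "female partner who becomes pregnant while the male patient is in the study".
- Arm: "This applies only to male patients who receive ensifentrine".
- Deadline: once the partner has consented, the investigator must record the information and "submit it to the Sponsor within 24 hours of learning of the partner's pregnancy".

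Other sections bear on these conditions:

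- Blinding. Under Section 6.4 the IRT shows all site staff, including the unblinded dosing staff, blinded reports only. Section 6.5 allows the blind to be broken only where emergency treatment requires it, and otherwise keeps it until database lock.
- Male contraception. The contraception guidance in 11.8 runs "from the first dose up to 30 days after the last dose of study medication", and the ban on sperm donation ends at the same point. Inclusion criterion 3 has the same 30-day end.
- Female patients. Section 8.7.5 collects pregnancies after the start of study medication "until 30 days after the last dose of blinded study medication", with no arm restriction. The paragraph on female patients in 11.8 refers only to pregnancies during participation.
- Study exit. Section 4.1 states: "Patients completing treatment will complete a Follow-Up within 4 to 10 days of the last scheduled study visit". The same interval applies after an early termination visit, and Section 4.4 treats the follow-up contact as the end of a patient's participation.

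**The concern.** The arm condition asks the investigator to act on information that the design withholds. Sites may resolve this differently, so whether a partner pregnancy is recorded could depend on how the site reads one sentence. Data not collected at the time may not be recoverable after database lock.

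The time condition ends capture of new partner pregnancies at study exit, although men are asked to take precautions for longer. The adverse reproductive findings in Section 2.3 came from dosed male rats and include "lower sperm motility and higher abnormal sperm". Partner pregnancies are therefore reports that a sponsor would want complete, yet their collection rule is narrower than the one for female patients.

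**Working it through.** The plan states no figure on this point, so there is none to reproduce. The check compares the rules and then counts days.

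**Can the arm condition be applied?**

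1. The deadline is 24 hours from learning of the pregnancy (11.8).
2. Assignment is not available to site staff through the IRT (6.4), and a partner's pregnancy is not emergency treatment of the patient (6.5).
3. Assignment cannot be inferred from the design. With 500 patients on ensifentrine and 300 on placebo, the chance that a given man is on ensifentrine is 500 / 800 = 62.5%.

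The condition therefore cannot be applied during data collection. It could be applied after database lock, but only to reports already collected.

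**How much of the 30-day period is uncovered?**

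Let D be the number of days from last dose to the follow-up contact. Uncovered days = max(0, 30 − D).

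- *Completer.* The last dose is on the morning of the Week 24 visit (SAP 15.1.1), so D is 4 to 10. The result is 30 − 10 = 20 to 30 − 4 = 26 days, or 20/30 = 67% to 26/30 = 87% of the period.
- *Early termination.* If the last dose was L days before the termination visit, D is L + 4 to L + 10. The documents do not give L, so the values below are assumptions.

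| Assumed L (days) | Uncovered days |
|---|---|
| 0 | 20 to 26 |
| 7 | 13 to 19 |
| 14 | 6 to 12 |
| 20 | 0 to 6 |

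- *Stops medication but stays in the study (Section 7.2).* If he remains for at least 30 days after the last dose, the uncovered interval is 0.

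**Does another section fill the gap?**

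- Section 8.7.5 names female patients only.
- Section 8.7.1 covers SAEs that the investigator learns of after discharge and considers reasonably related. It does not provide for collecting a partner's pregnancy.
- The post-study bullet in 11.8 stands under female patients and concerns related SAEs.

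**The case against.** The strongest reply is that a sensible site would collect the information for any male patient, as the opening sentence of the paragraph suggests, and leave the sponsor to sort by arm after lock. That would work, but it means disregarding the sentence that follows, and nothing tells sites to do so. Nor can the unblinded dosing staff settle the question: Section 6.4 keeps them apart from study conduct and bars discussion of the medication's appearance, so using them to sort reports would pass arm information to the investigator.

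It is also fair to say that the 30 days are a contraception and sperm-donation period. The protocol does not call them a risk window or a surveillance period for partners. That stands. The case for alignment is consistency with these precautions and with the collection window for female patients.

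Four stronger readings are tempting, and the documents do not support them.

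- *These reports would test the rat signal, and a placebo comparison is lost.* Reduced fertility and pre-implantation loss would not appear as reported pregnancies. Patients are aged 40 to 80, and men with partners of childbearing potential must be abstinent or use a condom plus a partner method failing in under 1% per year. SAP Section 17 plans no summary of pregnancies. Section 2.3 also places the effects at the highest dose, 15.5 mg/kg/day, and reports no adverse effect at 5.75 mg/kg/day, 20.5 times the maximum recommended human dose based on AUC.
- *Partner-pregnancy data stop at study exit.* Only capture of new pregnancies stops. A pregnancy that began in the study is followed to outcome, generally until no more than 6 to 8 weeks past the due date.
- *The rule calls for unblinding.* Section 11.8 neither asks for nor authorises it. Unblinding is one of three ways in which a site might resolve the conflict.
- *Every man has a 20-to-26-day gap.* That range holds only when the last dose is on the day of the final visit.

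**Conclusion.** The point holds as a defect in case-level safety reporting. The arm restriction conflicts with the blind and cannot be followed as written; that conclusion rests on the text alone. The window mismatch is also real. It is 20 to 26 of 30 days for a man dosed up to his final visit, shrinks day for day with earlier stopping, and is nil for a man who stays in the study 30 days or more after his last dose. The number of men affected cannot be stated, because the documents give neither the male share nor the number with partners of childbearing potential. Expected pregnancies are very few. No endpoint, power figure or efficacy analysis is affected.

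**What to change.** In Section 11.8:

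1. Delete the sentence that limits collection to men on ensifentrine, so that partner pregnancies are collected for all treated men regardless of arm.
2. Reconcile the collection window, for male patients' partners and for female patients, with Section 8.7.5 and the 30-day post-dose period.
3. At the existing follow-up contact, remind patients to report any pregnancy arising later within that period. No additional call is needed.

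The cost is amendment wording and one prompt at a contact already scheduled. The downside is a few additional placebo-arm reports, each with the partner consent that 11.8 already requires. No visit, test or treatment rule changes.
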